**Appendix D. International Myeloma Working Group Uniform Response Criteria for Multiple Myeloma (IMWG-URC)**

Response	Subcategory a	Multiple Myeloma Response Criteria
	sCR b	

• CR as defined below and

• Normal SFLC ratio and

• Absence of clonal cells in bone marrowc by immunohistochemistry or immunofluorescencec

	CR b	

• Negative immunofixation on the serum and urine and

• Disappearance of any soft tissue plasmacytomas and

• < 5% plasma cells in bone marrowc

	VGPR b	

• Serum and urine M-protein detectable by immunofixation but not on electrophoresis or

• <math>\geq 90\%</math> reduction in serum M-protein with urine M-protein level <math>< 100</math> mg/24 hours

• If the serum and urine M-protein are not measurable, a decrease of <math>\geq 90\%</math> in the difference between the involved and unininvolved FLC levels required in place of the M-protein criteria. However, documentation of VGPR requires collection and analysis of 24 hour urine sample for UPEP and immunofixation and confirmed to be negative.

• If present at Baseline, a <math>\geq 50\%</math> reduction in the size of soft tissue plasmacytomas is also required.

	PR b	

• <math>\geq 50\%</math> reduction of serum M-protein and reduction in 24-hour urinary M-protein by <math>\geq 90\%</math> or to <math>< 200</math> mg/ 24 h

• If the serum and urine M-protein are unmeasurable, a <math>\geq 50\%</math> decrease in the difference between involved and unininvolved FLC levels is required in place of the M-protein criteria.

• If serum and urine M-protein are not measureable, and serum free light assay is also not measureable, <math>\geq 50\%</math> reduction in plasma cells is required in place of M-protein, provided baseline bone marrow cell percentage was <math>\geq 30\%</math>

• If present at Baseline, a <math>\geq 50\%</math> reduction in the size of soft tissue plasmacytomas is also required

Stable disease		

• Not meeting criteria for CR, VGPR, PR, or PD

Page 1 of 2

Footnotes defined on last page of this table

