Response	Subcategory a	Multiple Myeloma Response Criteria
PD b		

• Any one or more of the following:

• Increase of <math>\geq 25\%</math> from lowest response value in:

○ Serum M-component and/or (the absolute increase must be <math>\geq 0.5</math> g/dL)

○ Urine M-component and/or (the absolute increase must be <math>\geq 200</math> mg/24 h)

○ Only in patients without measurable serum and urine M-protein levels; the difference between involved and uninvolved FLC levels. The absolute increase must be <math>>10</math> mg/dL

○ Bone marrow plasma cell percentages (absolute percentage must be <math>\geq 10\%</math>)

• Definite development of new bone lesions or soft tissue plasmacytomas or definite increase in the size of existing bone lesions or soft tissue plasmacytomase, f, g

• Development of hypercalcemia (corrected serum calcium <math>> 11.5</math> mg/dL or 2.65 mmol/L) that can be attributed solely to the plasma cell proliferative disorder

Page 2 of 2

Source: Durie 2006; Rajkumar 2011 (*modified for protocol purposes*).

CR = complete response; sCR = stringent complete response; FLC = serum light chain; MR = minor response; PD = progressive disease; PR = partial response; SFLC = serum free light chain; VGPR = very good partial response.

Note:

a Patients with measurable disease in both serum (SPEP) and urine (UPEP) at study entry are required to meet response criteria in both UPEP and SPEP in order to qualify for a MR or better. Conversely, it should be noted that criteria for PD only needs to be met, and confirmed, in one parameter. For patients without measurable protein on UPEP at Baseline, UPEP will need to be repeated to confirm a response.

b All response categories (CR, sCR, VGPR, PR) require 2 consecutive assessments made at any time before the institution of any new therapy, as well as no known evidence of progressive or new bone lesions if radiographic studies were performed. Radiographic studies are not required to satisfy these response requirements. Bone marrow, plasmacytoma, and skeletal survey assessments are not required to be confirmed by repeat testing. SD requires a duration of  $\geq 6$  weeks.

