c Presence/absence of clonal cells is based upon the  $\kappa/\lambda$  ratio. An abnormal  $\kappa/\lambda$  ratio by immunohistochemistry and/or immunofluorescence requires a minimum of 100 plasma cells for analysis. An abnormal ratio reflecting presence of an abnormal clone is  $\kappa/\lambda$  of  $> 4:1$  or  $< 1:2$ .

d Determination of PD while on study requires 2 consecutive assessments made at any time before classification of PD and/or the institution of new therapy. Serum M-component increases of  $\geq 1$  g/dL from nadir are sufficient to define progression if starting M-component is  $\geq 5$  g/dL.

e Plasmacytomas: A definite increase in the size is defined as a  $\geq 50\%$  increase as measured serially by the sum of the products of the cross-diameters of the measurable lesion. A plasmacytoma is considered measurable if the longest diameter is at least 1 cm and the product of the cross diameters is at least 1 cm^2. Plasmacytomas of lesser size will be considered non-measurable.

f The requirement for bi-directional measurements applies only to plasmacytomas.

g The plasmacytoma specifications for PD are based on interpretation of the IMWG-URC and practical considerations for study execution.

Definition of Minimal Response per EBMT Criteria

Minimal Response	
Response Subcategory	Response Criteria
MR a	≥ 25 but < 49% reduction in serum M-protein and a 50–89% reduction in 24-hour urinary M-protein, which still exceeds 200 mg per 24 h
	If the serum and urine M-protein are not measurable, a decrease of 25%–49% in the difference between involved and uninvolved FLC levels is required in place of the M-protein criteria.
	For patients with nonsecretory myeloma only, 25–49% reduction in plasma cells in a bone marrow aspirate and on trephine biopsy, if biopsy is performed
	25–49% reduction in the size of soft tissue plasmacytomas (by radiography or clinical examination)

Sources: [Bladé 1998](#); [Kyle 2009](#).

EBMT = European Group for Blood and Marrow Transplantation; FLC = free light chain; MR = minimal response.

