- **Patients who are alive without documented disease progression, and have withdrawn consent at the time of analysis will be censored at the date of the last disease assessment before withdrawal of consent.**
- **Patients who have started an anti-cancer therapy other than the study treatment prior to documentation of disease progression will be censored at the date of the last disease assessment prior to start of new therapy.**

Best Overall Response (BOR)

The best response that a subject achieved during study where the responses are ranked from best to worst as follows: stringent complete response [sCR], complete response [CR], very good partial response [VGPR], and partial response [PR], minimal response [MR], stable disease [SD] and progressive disease [PD] (all according to Revised International Myeloma Working Group Uniform Response Criteria [IMWG-URC])

Overall Response Rate (ORR)

Proportion of subjects with BOR of sCR, CR, VGPR or PR.

Duration of Grade II GI Toxicity

Duration of Grade II GI toxicity is defined as the number of days between the start date through to the subsequent end date of the Grade II GI toxicity, or where applicable date of censoring [end date of the Grade II GI toxicity or date of censoring – start date of the Grade II GI toxicity +1]. Subjects whose Grade II GI toxicity do not end while on study will be censored at the date when they are last on study. Subjects who do not experience Grade II GI toxicity will be excluded from the analysis of duration of Grade II GI toxicity. **The intermittent adverse events will be excluded from the analysis of duration of Grade II GI toxicity, and not to be counted as one ongoing adverse event.**

Duration of Grade III or above GI Toxicity

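### Appendix D's minimal-response row has upper limits, so a subject measurable in both serum and urine can score stable disease after a larger fall than one that scores minimal response

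*Protocol*

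**What the plan says.** Protocol Appendix D has two tables. In the IMWG table, the PR row asks for at least a 50% "reduction of serum M-protein and reduction in 24-hour urinary M-protein by" at least 90%, or to below 200 mg/24 h. The SD row is the remainder: "Not meeting criteria for CR, VGPR, PR, or PD". Footnote a adds that subjects with measurable disease in both serum and urine "are required to meet response criteria in both UPEP and SPEP in order to qualify for a MR or better".

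MR comes from the second table, which is headed as following EBMT criteria: "≥ 25 but < 49% reduction in serum M-protein and a 50–89% reduction in 24-hour urinary M-protein, which still exceeds 200 mg" per 24 h. Where neither M-protein is measurable, "a decrease of 25%–49% in the difference between involved and uninvolved FLC levels is required". The marrow and plasmacytoma lines use the same 25–49% range. MR must be seen at two consecutive assessments.

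SAP Section 5 makes MR a level of BOR. The lower end of its ranking reads "partial response [PR], minimal response [MR], stable disease [SD] and progressive disease [PD", and the SAP attributes the whole list to IMWG. It counts only PR or better towards ORR. Inclusion criterion 105 accepts urine M-protein of 200 mg/24 h or more as measurable.

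**The concern.** The SAP uses these categories as an ordered scale, so a larger fall in M-protein should never earn a lower level. The MR row does not guarantee that. It describes a box, with an upper as well as a lower limit in each compartment, and PR begins only when both compartments are past their own thresholds. A subject who leaves the box upwards in one compartment without reaching PR in the other has nowhere to go but SD.

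At stake is the MR/SD split in the BOR summaries by formulation and dose cohort. Whoever programs BOR must also settle these mixed cases somehow, and neither document records a rule for doing so.

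**Working it through.** The plan gives no figure to reproduce, so the check applies the Appendix D rows literally to example subjects.

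**Rules, for a subject measurable in both compartments.** S = serum fall, U = urine fall, R = residual urine = baseline × (1 − U).
- PR: S ≥ 50% and (U ≥ 90% or R < 200 mg/24 h).
- MR: 25% ≤ S < 49%, and 50% ≤ U ≤ 89%, and R > 200 mg/24 h.
- SD: everything else that is not PD.

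Assumptions: no progression, no plasmacytoma, M-protein still visible on electrophoresis, and SD lasting the six weeks that Appendix D requires. The baseline urine values are illustrative.

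| Case | S | Urine, mg/24 h (U) | Why not PR | Why not MR | As written | Lower limits only |
|---|---|---|---|---|---|---|
| 1 | 30% | 1000 to 400 (60%) | serum, urine | meets MR | MR | MR |
| 2 | 60% | 1000 to 300 (70%) | urine | serum over limit | SD | MR |
| 3 | 80% | 3000 to 450 (85%) | urine | serum over limit | SD | MR |
| 4 | 30% | 5000 to 250 (95%) | serum | urine over 89% | SD | MR |
| 5 | 30% | 1000 to 50 (95%) | serum | urine over 89%, R not above 200 | SD | MR |
| 6 | 30% | 1000 to 200 (80%) | serum | R not above 200 | SD | MR |
| 7 | 49% or 49.5% | 1000 to 300 (70%) | serum, urine | serum over limit | SD | MR |
| 8 | 30% | 400 to 160 (60%) | serum | R not above 200 | SD | MR |

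Cases 2 and 3 fell further than case 1 in both compartments and rank lower. The last column uses S ≥ 25% and U ≥ 50%, not meeting PR or better. No case moves into or out of PR or VGPR, so ORR is unchanged.

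**Gaps.** A serum fall of 49% to under 50% fits neither MR nor PR. The free-light-chain (FLC) line behaves differently: 49% is MR, 49.5% is SD and 50% is PR. Urine has a similar gap between 89% and 90% (S = 48%, urine 5000 to 525, U = 89.5%, gives SD). Rounding to whole percentages closes the FLC and urine gaps. It does not close the serum gap, because the serum line excludes 49% itself.

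**Low baseline urine.** If baseline is 400 mg/24 h or less and U ≥ 50%, then R ≤ 400 × 0.5 = 200, which does not exceed 200. Criterion 105 counts 200 mg/24 h as measurable, so a subject with baseline urine of 200 to 400 mg/24 h and measurable serum can never be MR.

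**Upper bound on numbers.** Protocol Section 5.5.5 reports PR or better in 20 of 28 IR and 3 of 8 GR evaluable subjects. Taking both figures as OPomd, 28 − 20 = 8 and 8 − 3 = 5, so 13 of 36 were below PR. Those 13 include progressive disease, true SD and true MR. Affected subjects are a subset with discordant falls, a gap value or low baseline urine, and its size is not given.

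**The case against.** The other side has several fair points.

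- **The plan adopts a named standard.** Whether the 49% limit is a slip or the source's wording cannot be settled from these documents. Citing a source still does not make the scale ordered, and the SAP ranks it as if it were.
- **Footnote a can be read more kindly:** each compartment must reach at least MR level, so PR level in one and MR level in the other gives MR. That is a sensible rule, but the text does not state it, and the MR row's explicit upper limits point the other way.
- **The examples are single visits, while BOR is the best response over the study.** This stands. A subject who holds a confirmed MR and later moves outside the box keeps MR as BOR. Passing through the box at one visit is not enough, because MR needs two consecutive assessments.
- **The SD row does not exclude MR.** A reader might infer that every MR subject could equally be reported as SD. The SAP ranking already settles that overlap in favour of MR.
- **Cohort comparison.** A reader might infer that comparisons between doses or formulations are distorted. Efficacy is among the data the dose level review team considers, but BOR is only summarised, the analyses are hypothesis generating, and no rule uses MR against SD. In OPomd cohorts of 4 to 10 subjects, one reclassified subject is 1/10 to 1/4, or 10 to 25 points. That is only the reciprocal of the cohort size, not an estimate of any effect.
- **Serum-only disease.** If the serum part is applied alone, a fall of 50% or more is PR and only the 49–50% gap remains. This also stands: the upper-limit problem needs disease measurable in both compartments.

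**Conclusion.** The point holds on the text as written. The MR row is not monotone for subjects measurable in both serum and urine, it leaves a serum gap at 49% to under 50% that disagrees with the other MR lines, and it makes MR unreachable for dual-measurable subjects with baseline urine of 200 to 400 mg/24 h.

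Its reach is small. It touches only the MR/SD split of BOR, and only in subjects with no confirmed MR at another time and no PR. How many there are cannot be determined from the documents. A reader might infer that the reported response rate is wrong, and the documents do not support that: ORR, DOR and TTR start at PR, PFS uses progression or death, and the MTD uses DLTs. The conclusion rests on reading the MR row and footnote a literally. Under the kinder reading of footnote a, the mixed PR-level/MR-level cases resolve to MR, but the serum gap remains. This is worth correcting and is low in priority.

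**What to change.** In Appendix D and the SAP's BOR derivation, define MR by lower limits only and as not meeting PR or better. In each compartment measurable at baseline, require a serum fall of at least 25% and a urine fall of at least 50%, or a urine value meeting the PR urine criterion. Use a lower limit of 25% with no upper limit for the FLC, marrow and plasmacytoma lines; leaving an upper limit on plasmacytomas would recreate the problem there.

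The PR-urine clause lets a small urine fall count, for example 210 to 199 mg/24 h (11/210, about 5%). The PR row already accepts that value, so refusing it for MR would be inconsistent.

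At minimum, change the serum limit from under 49% to under 50%, and state that PR level in one compartment with MR level in the other is MR. This shorter version still leaves a residual of exactly 200 mg/24 h unassigned, along with the 89–90% urine gap and the 49–50% FLC gap unless percentages are rounded.

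Also correct the SAP so that MR is attributed to the protocol's EBMT table, not IMWG. Adding MR to the SD row's exclusions is optional tidying.

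The change needs no new data, but it is more than wording. Protocol Section 5.5.5 already reports results to a cutoff of 02 December 2019, and the final analysis is to use the primary methods. So document the change as post hoc, re-derive BOR, list every subject whose BOR changes, and show BOR under both definitions.

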## Appendix E. ECOG Performance Status and NYHA Classification

### Eastern Cooperative Oncology Group (ECOG) Performance Status

0. Fully active, able to carry out all pre-disease performance without restriction
1. Restricted in physically strenuous activity, but ambulatory and able to carry out work of a light or sedentary nature (eg, light housework, office work)
2. Ambulatory and capable of all selfcare, but unable to carry out any work activities. Up and about more than 50% of waking hours
3. Capable of only limited selfcare, confined to bed or chair more than 50% of waking hours
4. Completely disabled. Cannot carry out any selfcare. Totally confined to bed or chair
5. Dead

### New York Heart Association Functional Classification

1. Class I No limitation of physical activity. Ordinary physical activity does not cause undue fatigue, palpitation or dyspnea.
2. Class II Slight limitation of physical activity. Comfortable at rest, but ordinary physical activity results in fatigue, palpitation or dyspnea.
3. Class III Marked limitation of physical activity. Comfortable at rest, but less than ordinary activity causes fatigue, palpitation or dyspnea.
4. Class IV Unable to carry out any physical activity without discomfort. Symptoms of cardiac insufficiency may be present even at rest. If any physical activity is undertaken, discomfort is increased.

**Appendix F. Definition of Relapsed or Refractory Disease and Line of Therapies**

**Relapsed disease** is defined as progression occurs in the absence of therapy.

**Refractory disease** is defined as disease that is nonresponsive while on primary or salvage therapy, or progresses within 60 days of last therapy.

**A line of therapy** is defined as one or more cycles of a planned treatment program.

This may consist of one or more planned cycles of single-agent therapy or combination therapy, as well as a sequence of treatments administered in a planned manner. For example, a planned treatment approach of induction therapy followed by autologous stem cell transplantation, followed by maintenance is considered one line of therapy. A new line of therapy starts when a planned course of therapy is modified to include other treatment agents (alone or in combination) as a result of disease progression, relapse, or toxicity. A new line of therapy also starts when a planned period of observation off therapy is interrupted by a need for additional treatment for the disease

(Rajkumar, 2011).

#### Appendix G. Peripheral Neuropathy Assessment

TNSr Items	0	1	2	3	4
Symptom extension (tingling, numbness, neuropathic pain) a	None	Symptoms limited to fingers or toes	Symptoms extend to ankle or wrist	Symptoms extend to knee or elbow	Symptoms above knees or elbows or functionally Disability
Pin sensibility	Normal	Reduced in fingers/toes	Reduced up to wrist/ankle	Reduced up to elbow/knee	Reduced up to above elbow/knee
Vibration sensibility	Normal	Reduced in fingers/toes	Reduced up to wrist/ankle	Reduced up to elbow/knee	Reduced up to above elbow/knee
Strength b	Normal	Mild weakness	Moderate weakness	Severe Weakness	Paralysis
Tendon reflexes	Normal	Ankle reflex reduced	Ankle reflex absent	Ankle reflex absent/others reduced	All reflexes absent

a The worse score of the 3 subcomponents (tingling/paresthesia, numbness, and neuropathic pain proximal extension) was used as the subjective symptom extension score.

b The muscle with the worse score is used as the strength score (toe, ankle, wrist and finger extensors and flexors, quadriceps, hamstrings, biceps, and triceps). TNSr and pain items were adapted with permission [Lavoie Smith, 2010]

---

## Appendix H. Pomalidomide Risks of Fetal Exposure, Pregnancy Testing Guidelines, and Acceptable Birth Control Methods

### Risks Associated with Pregnancy

Pomalidomide was found to be teratogenic in a developmental study in rabbits. Pomalidomide is an analogue of thalidomide. Thalidomide is a known human teratogen that causes severe life-threatening human birth defects. If pomalidomide is taken during pregnancy, it may cause birth defects or death to an unborn baby.

### Criteria for Females of Childbearing Potential (FCBP)

This protocol defines a female of childbearing potential as a sexually mature woman who: 1) has not undergone a hysterectomy or bilateral oophorectomy or 2) has not been naturally postmenopausal (amenorrhea following cancer therapy does not rule out childbearing potential) for at least 24 consecutive months (ie, has had menses at any time in the preceding 24 consecutive months).

### Counseling

For an FCBP, pomalidomide is contraindicated unless all of the following are met (ie, FCBP must be counseled concerning the following risks and requirements prior to the start of pomalidomide study therapy):

- She understands the potential teratogenic risk to the unborn child
- She understands the need for effective contraception, without interruption, 28 days before starting study treatment, throughout the entire duration of study treatment, dose interruption, and 28 days after the End of Study Treatment
- She should be capable of complying with effective contraceptive measures
- She is informed and understands the potential consequences of pregnancy and the need to notify her study doctor immediately if there is a risk of pregnancy
- She understands the need to commence the study treatment as soon as pomalidomide is dispensed following a negative pregnancy test
- She understands the need and accepts to undergo pregnancy testing based on the frequency outlined in this protocol
- She acknowledges that she understands the hazards and necessary precautions associated with the use of pomalidomide

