- Negative HBsAg and positive for hepatitis B core antibody: hepatitis B virus DNA by polymerase chain reaction (PCR) is necessary. Detectable hepatitis B virus DNA suggests occult hepatitis B
- Positive Hepatitis C virus antibody (HCVAb): hepatitis C virus RNA by PCR is necessary. Detectable hepatitis C virus RNA suggests chronic hepatitis C

217 History of clinically significant GI hemorrhage (Grade  $\geq$  2) in the 6 months prior to study day 1, unless agreed upon by the investigator and the Amgen Medical Monitor

218 Known positive results for Human Immunodeficiency Virus (HIV)

219 Unresolved toxicities from prior anti-tumor therapy, defined as not having resolved to Common Terminology Criteria for Adverse Events (CTCAE) version 4.03 Grade 1, or to levels dictated in the eligibility criteria with the exception of Grade 2 peripheral neuropathy, alopecia or toxicities from prior anti-tumor therapy that are considered irreversible (defined as having been present and stable for  $>$  4 weeks may be allowed if they are not otherwise described in the exclusion criteria AND there is agreement to allow by both the investigator and the Amgen Medical Monitor)

220 Anti-tumor therapy (chemotherapy, antibody therapy, molecular targeted therapy, or investigational agent) within 28 days or 5 half-lives whichever is shorter prior to study day 1.

221 Prior systemic radiation therapy must have been completed at least 28 days before study day 1. Prior focal radiotherapy completed at least 14 days before study day 1

222 Major surgery within 28 days prior to study day 1

223 Females of reproductive potential who are unwilling to use two methods of contraception, one highly effective and one additional effective contraception

method while on study through 30 days after receiving the last dose of study drug. Males unwilling to always use latex or synthetic condom during any sexual contact with females of reproductive potential while on study through 90 days after receiving the last dose of study drug. Acceptable highly effective methods of birth control are defined:

- Combined (estrogen and progestogen containing) hormonal contraception associated with inhibition of ovulation:
  - Oral
  - Intravaginal
  - Transdermal
- Progestogen-only hormonal contraception associated with inhibition of ovulation:
  - Oral
  - Injectable
  - Implantable
- Intrauterine device (IUD)
- Intrauterine hormone-releasing system (IUS)
- Bilateral tubal occlusion
- Vasectomized partner

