- Sexual abstinence
- Males must also refrain from donating sperm for at least 90 days after the last dose of oprozomib

224 Female who is breastfeeding or who plans to breastfeed while on study through 30 days after receiving the last dose of study drug

225 Female with a positive pregnancy test

226 Female planning to become pregnant while on study through 30 days after receiving the last dose of study drug

227 Known hypersensitivity to any immunomodulatory drugs (IMiDs) or their formulation excipients, including rash

228 Known hypersensitivity or intolerance to dexamethasone or its formulation excipients

229 Prior exposure to oprozomib

230 History or evidence of any other clinically significant disorder, condition or disease that, in the opinion of the investigator or Amgen medical monitor, if consulted, would pose a risk to subject safety or interfere with the study evaluation, procedures or completion

231 Prior use of pomalidomide if subjects required pomalidomide dose reduction or pomalidomide discontinuation due to toxicity

232 Subjects known to have any of the following disorders will be excluded unless agreed upon by the investigator and the Amgen Medical Monitor:

- Galactosemia (deficiency in galactose-1-phosphate-uridyltransferase or UDP-galactose-4-epimerase or galactokinase; Fanconi-Bickel-Syndrome)
- hereditary lactase deficiency
- glucose-galactose malabsorption

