### Contraception

Females of reproductive potential must commit either to abstain continuously from heterosexual sexual intercourse or to use 2 methods of effective contraception simultaneously (1 highly effective form of contraception—tubal ligation, intrauterine device [IUD], hormonal [birth control pills, injections, hormonal patches, vaginal rings or implants] or partner's vasectomy and 1 additional effective contraceptive method—male latex or synthetic condom, diaphragm, or cervical cap). Contraception must begin 4 weeks prior to initiating treatment and continue during therapy, dose interruptions, and for 30 days after discontinuation of therapy. Reliable contraception is indicated even where there has been a history of infertility, unless this is due to hysterectomy. Females of reproductive potential should be referred to a qualified provider of contraceptive methods, if needed. Additional details are provided in Pomalidomide Risks of Fetal Exposure, Pregnancy Testing Guidelines and Acceptable Birth Control Methods ([Appendix H](#)), Pomalidomide Education and Counseling Guidance Document ([Appendix I](#)), and Pomalidomide Information Sheet for Subjects Enrolled in Clinical Research Studies ([Appendix J](#)).

Females of reproductive potential must have 2 negative pregnancy tests before initiating study treatment. The first test should be performed within 10 to 14 days of study treatment and the second test should be performed within 24 hours before study treatment. Once treatment has started and during dose interruptions, pregnancy testing for female subjects of reproductive potential should occur weekly during the first 4 weeks of treatment. Pregnancy testing should be repeated every 4 weeks thereafter for female subjects with regular menstrual cycles. For female subjects with irregular menstrual cycles,  $\pm$  7 days of a 28-day cycle, pregnancy testing should be performed every 2 weeks. Pregnancy testing and counseling should be performed if a subject misses her period or if there is any abnormality in her menstrual bleeding. Study treatment must be discontinued during this evaluation.

---

Postmenopausal females (> 45 years old and without menses for > 2 years) and surgically sterilized females are exempt.

Male subjects must use an effective barrier method of contraception during the study and for 90 days following the last dose if sexually active with a female of childbearing potential.

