**To be completed prior to each dispensing of pomalidomide**

**Do Not Dispense pomalidomide if:**

- The patient is pregnant.
- No pregnancy tests were conducted for a FCBP.
- The patient states she did not use TWO reliable methods of birth control (unless practicing complete abstinence of heterosexual intercourse) [at least 28 days prior while taking pomalidomide, during dose interruption, and 28 days after discontinuation of pomalidomide].

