**FCBP**

1. **I verified that the required pregnancy tests performed are negative.**
2. **I counseled FCBP regarding the following:**
  - Potential fetal harm: If pomalidomide is taken during pregnancy, it may cause birth defects or death to any unborn baby. Females are advised to avoid pregnancy while taking pomalidomide. The teratogenic potential of pomalidomide in humans cannot be ruled out. Females of childbearing potential must agree not to become pregnant while taking pomalidomide.
  - Using TWO reliable methods of birth control at the same time or complete abstinence from heterosexual intercourse [at least 28 days prior, while taking pomalidomide, during dose interruption, and 28 days after discontinuation of pomalidomide].
  - Continuation of TWO reliable methods of birth control or complete abstinence if therapy is interrupted.
  - That even if she has amenorrhea she must comply with advice on contraception.
  - Use of one highly effective method and one additional method of birth control AT THE SAME TIME. The following are examples of highly effective and additional effective methods of contraception:

- Highly effective methods:
  - Intrauterine device (IUD)
  - Hormonal (birth control pills, injections, implants)
  - Tubal ligation
  - Partner's vasectomy
- Additional effective methods:
  - Male condom
  - Diaphragm
  - Cervical cap
- Pregnancy tests before and during treatment, even if the patient agrees not to have reproductive heterosexual intercourse. Two pregnancy tests will be performed prior to receiving study drug, one within 10–14 days and the second within 24 hours of the start of pomalidomide.
- Frequency of pregnancy tests to be done:
  - Every week during the first 28 days of this study and a pregnancy test every 28 days during the patient's participation in this study if menstrual cycles are regular or every 14 days if cycles are irregular.
  - If the patient missed a period or has unusual menstrual bleeding.
  - When the patient is discontinued from the study and at Day 28 after study drug discontinuation if menstrual cycles are regular. If menstrual cycles are irregular, pregnancy tests will be done at discontinuation from the study and at Days 14 and 28 after study drug discontinuation.
- Stop taking pomalidomide immediately in the event of becoming pregnant and to call their study doctor as soon as possible.
- NEVER share pomalidomide with anyone else.

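### Female contraception: the counselling text in Appendices H and I gives an earlier end date than the 30 days required by section 9.6 and criterion 223

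*Protocol*

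**What the plan says.** Two places set the rule for women.

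- Section 9.6, Contraception: "Contraception must begin 4 weeks prior to initiating treatment and continue during therapy, dose interruptions, and for 30 days after discontinuation of therapy".
- Section 7.2, criterion 223: contraception "while on study through 30 days after receiving the last dose of study drug".

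Three places in the counselling material give a different end.

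- Appendix H, Counseling: "28 days before starting study treatment, throughout the entire duration of study treatment, dose interruption, and 28 days after the End of Study Treatment".
- Appendix I, list of reasons not to dispense pomalidomide: "28 days after discontinuation of pomalidomide".
- Appendix I, counselling for women of childbearing potential: "at least 28 days prior, while taking pomalidomide, during dose interruption, and 28 days after discontinuation of pomalidomide".

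Other text bears on how these fit together.

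- Sections 9.3.1.1 and 9.3.2.2 let a subject stop pomalidomide permanently and stay on oprozomib with dexamethasone.
- Section 9.2 defines study treatment as any combination of the three drugs.
- Appendix H, Contraception, covers the whole of study participation (item 2) and sets a minimum of 28 days after treatment (item 4).
- Section 6.5.2 places the end-of-study visit 30 to 37 days after the last study treatment.

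**The concern.** The counselling list and the dispensing form are what site staff work through with the woman. Both give 28 days with no wording to mark it as a minimum, against 30 in the rule. Appendix I also counts from a different event, the end of pomalidomide rather than the end of study treatment. The form is completed before each dispensing of pomalidomide. Once that drug stops, nothing prompts the form again, and the last end date it gave the woman was tied to the wrong drug.

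The subject is fetal exposure. Appendix H warns that pomalidomide in pregnancy may cause malformation or fetal death. The protocol also treats oprozomib exposure as relevant in its own right: section 12.3 requires reporting of pregnancies through 30 (+7) days after the last oprozomib dose. Instructions on this subject should not disagree with one another.

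**Working it through.** No sample size, error rate or estimate is involved. The check sets the texts side by side and counts days.

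**Inputs**

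- Rule: 30 days after the end of therapy (section 9.6) or after the last dose (criterion 223).
- Appendix H, Counseling: 28 days after the end of study treatment.
- Appendix I: 28 days after stopping pomalidomide.
- Appendix H, Contraception: throughout study participation, and at least 28 days after treatment.
- End-of-study visit: day 30 to 37 after the last study treatment (section 6.5.2).

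**Case 1: all drugs stop on the same day**

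Rule minus counselling text: 30 − 28 = 2 days, for both Appendix H Counseling and Appendix I.

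**Case 2: pomalidomide stops and oprozomib continues for T more days**

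- Appendix I end: day 28 after pomalidomide stops.
- Rule: day T + 30.
- Gap: (T + 30) − 28 = T + 2 days.

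The Appendix I date falls during study treatment whenever T is more than 28. As an illustration, if oprozomib runs for two further 28-day cycles and T is taken as 2 × 28 = 56, the gap is 56 + 2 = 58 days. The documents do not say how long women stay on oprozomib after stopping pomalidomide, so T is an assumption. Appendix H Counseling is not affected by T, because it counts from the end of study treatment, which includes oprozomib. Its gap stays at 2 days.

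**Backstop**

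Item 2 of Appendix H, Contraception, applies throughout study participation. The earliest end-of-study visit is day 30, so for a woman who attends it and follows item 2 the shortfall is 30 − 30 = 0 days.

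**Item 4 of Appendix H, Contraception**

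At least 28 days is a minimum. Thirty days satisfies it, so it does not conflict with section 9.6.

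**The case against.** The strongest reply is that no woman is released from the rule. Section 9.6 and criterion 223 both say 30 days. Appendix H, Counseling, runs to the end of all study treatment, and Appendix H, Contraception, covers study participation. The investigator must also confirm contraception at every visit. Appendix I is a pomalidomide form, so counting from pomalidomide is natural there, and its rules add to the study-wide rule rather than replace it. What a woman is told in total cannot be established either, because the consent form and the pomalidomide information sheet (Appendix J) are not in the text available for review.

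Most of this stands, and it is why the severity is low. It does not remove the discrepancy, because the backstops work only if the site and the woman follow text other than the counselling form.

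Three stronger readings are tempting, and the documents do not support them.

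- *That the protocol allows a woman on oprozomib to stop contraception.* It does not; section 9.6 and Appendix H still apply to her.
- *That criterion 223 lets women enter without the 4-week lead-in.* The criterion states no lead-in, but this is an omission. Section 9.6 and Appendix H (Counseling and Contraception) impose it.
- *That the abstinence wording is a safety gap.* Criterion 223 excludes "Females of reproductive potential who are unwilling to use two methods of contraception, one highly effective and one additional effective contraception" and lists "Sexual abstinence" among the highly effective methods, so read literally abstinence is only one of two required methods. Section 9.6 says "Females of reproductive potential must commit either to abstain continuously from heterosexual sexual intercourse or to use 2 methods of effective contraception simultaneously", and Appendices H and I also accept abstinence alone. The literal reading would be stricter, so it creates no unsafe exposure; at most a site is unsure whether an abstinent woman is eligible.

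**Conclusion.** The point holds as a low-severity correction. The counselling text in Appendix H and Appendix I gives women an earlier end to contraception than section 9.6 and criterion 223. The gap is 2 days when all drugs stop together. In Appendix I it is T + 2 days when oprozomib continues for T days after pomalidomide, and the stated end can then fall during study treatment. For a woman who attends the end-of-study visit and follows Appendix H, Contraception, it is 0 days.

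This assumes that the end-of-study visit is timed from the last study treatment, as section 6.5.2 states, and that some women of childbearing potential are still on treatment. Their number is not given. Nothing in the statistical analysis is affected.

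The eligibility wording matters only if enrolment is open. Section 5.5.5 already reports results for a primary analysis period, and section 6.5.2 places that analysis after target enrolment is complete, which suggests that enrolment has ended without stating it.

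**What to change.** In Appendix H, Counseling, and in both Appendix I passages for women, change the end of contraception to *at least 30 days after the last dose of study treatment (any of oprozomib, pomalidomide or dexamethasone)*. Item 4 of Appendix H, Contraception, may be aligned for consistency but does not need it.

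Confine the change to female contraception. The blood-donation periods stay as they are. The male condom text in Appendix I says 28 days, while section 9.6 and Appendix H, Male Subjects, require 90. Replacing 28 by 30 there would still leave it 90 − 30 = 60 days short; any correction of that text should go to 90.

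If enrolment is still open, also reword criterion 223 to *two methods, or complete abstinence*, to match section 9.6 and Appendix H. This clarifies eligibility and closes no safety gap.

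The cost is wording in the protocol and the counselling form, carried in an amendment that needs IRB/IEC approval (section 15.1). Section 9.6 already demands 30 days after therapy, so no woman would use contraception for longer than the protocol now requires.
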